Title of Study: Cognitive-Communication Screening and Early Therapy for Adults with Concussion/Mild Traumatic Brain Injury

Document Date: 09/13/2016

Type of Document: Study Protocol and Statistical Analyses

Procedures and Statistical Data Analyses: Patients will be evaluated for a concussion/mild traumatic brain injury at a local hospital in the emergency room. On the same day discharge papers, the patient will receive a description about the study and the PI contact information. During hospital follow-up phone calls to check on the status of the patients, they will be reminded of the study being conducted at the university and given the inclusionary/exclusionary criteria.

Subjects that voluntarily contact the PI and meet the inclusionary criteria will be scheduled for cognitive and communication screening at two weeks post-injury. The informed consent will be reviewed and signed prior to beginning the study. All subjects will receive monetary incentives for participation in the screening sessions.

The PI and her research assistants will audiotape all sessions to ensure that subjects' responses are scored and transcribed correctly. Inter-rater reliability of the scored items will be completed for 50% of the screenings conducted. All recordings will be destroyed one week following the sessions. The recordings will be restricted only to the PI and graduate research assistants. Next, the screening measures will be completed, and an education fact sheet will be reviewed with an emphasis on recovery.

At four weeks post-injury, the second screening session will be completed. Subjects who are below one standard deviation on screening scores will be randomly placed in either early treatment at one month post-injury or a waitlist control group which will receive the same therapy at two months post-injury. Subjects offered cognitive-communication therapy will participate in a one hour weekly session for four weeks. Prior to beginning therapy, a functional outcome measure will be administered. Intervention will consist of evidence-based therapies for working memory, executive function, and divided attention, environmental changes, and identification of problematic cognitive-communication situations. At the end of therapy, the same outcome measure will be completed.

Procedures for therapy will be the same for the waitlist control group. However, during the one month waiting period following the second screening, subjects will be given other activities that differ from the actual therapy activities.

All subjects will be contacted via phone at six months and 12 months post-injury to ensure resolution of cognitive-communication problems. If problems are identified later in recovery, the subjects will be instructed to contact their primary care physician for further referrals.

This is a longitudinal clinical study. Subjects will be followed for one year post-injury. Results from the screening measures at two and four weeks post-injury will be compared using a forward stepwise selection model procedure to determine which of the screening measures best detect persistent symptoms.

Finally, one tailed, non-paired t-tests will be used to compare pre- and post-therapy functional outcomes. Additionally, qualitative analyses will be completed on data related to the treatment.

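### The functional measure is tied to starting and finishing therapy, so not every randomised subject is measured, and the unpaired pre/post t-test compares different sets of people

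*Combined protocol and SAP*

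**What the plan says.** The combined protocol and SAP has one section, Procedures and Statistical Data Analyses. Four statements there bear on this point.

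- **First measurement:** "Prior to beginning therapy, a functional outcome measure will be administered".
- **Last measurement:** "At the end of therapy, the same outcome measure will be completed". Those receiving therapy "will participate in a one hour weekly session for four weeks".
- **Arms:** subjects are "randomly placed in either early treatment at one month post-injury or a waitlist control group which will receive the same therapy at two months post-injury". For the second arm, "Procedures for therapy will be the same for the waitlist control group".
- **Analysis:** "one tailed, non-paired t-tests will be used to compare pre- and post-therapy functional outcomes".

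The early arm's last measurement therefore falls at about eight weeks post-injury. On the natural reading, the waitlist's first measurement falls at about the same time. The later contacts ("All subjects will be contacted via phone at six months and 12 months post-injury to ensure resolution of cognitive-communication problems") are not stated to repeat the functional measure. The document gives no sample size, significance level, dropout allowance, analysis population or missing-data method. It does not say how subjects who stop or never start therapy are measured or analysed.

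**The concern.** Measurement follows therapy attendance rather than time since randomisation, which has two consequences.

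1. A subject who starts and then stops has only a pre-therapy score. An unpaired test accepts this without warning: the pre mean includes that subject and the post mean does not. If those who stop differ in function from those who stay, the two means differ even when nobody has changed.
2. A waitlist subject who leaves during the one-month wait may never be measured. Being in the data then depends on what happened after randomisation, so any comparison of the arms loses the protection of randomisation.

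Loss is a realistic prospect. Payment is stated for the screening sessions and not for the weekly therapy sessions, and some subjects may recover while waiting. A score that was never collected cannot be recovered at the analysis stage.

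**Working it through.** The plan has no figure to reproduce, so the check asks what the stated rule does when therapy has no effect.

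**Inputs from the document:** measurement at therapy start and end only; one-tailed unpaired t-test; two randomised arms.

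**Assumed inputs:** one-sided level 0.05; SD 1, with higher scores better; pre/post correlation ρ = 0.5; a fraction d = 0.2 lost; n = 20, 40 or 60 subjects starting therapy; correlation r between the tendency to stop and the pre-therapy score, from 0.5 to 1.

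**Step 1: no dropout.** An unpaired test on paired data has size 1 − Φ(1.645/√(1 − ρ)) = 1 − Φ(1.645/0.707) = 1 − Φ(2.33) ≈ 0.010. Simulation gives 0.012. The unpaired test starts out conservative, at about 1%.

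**Step 2: false gain from dropout.** Losing the lowest fraction d on a standard normal variable raises the mean of the rest by φ(z_d)/(1 − d) = 0.280/0.8 = 0.350. Completers' pre-therapy mean is then 0.350r, and their post-therapy mean is 0.350rρ. The test compares that post mean with the pre mean of all starters, which is 0.

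- r = 0.5: 0.350 × 0.5 × 0.5 = 0.087 SD
- r = 1: 0.350 × 1 × 0.5 = 0.175 SD (about 0.17 in samples of these sizes)

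**Step 3: false-positive rate.** Simulation of the planned test with no true effect:

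| n starting therapy | No dropout | 20% dropout, r = 0.5 | 20% dropout, r = 1 |
|---|---|---|---|
| 20 | about 1% | 3% | 6% |
| 40 | about 1% | 4% | 11% |
| 60 | about 1% | 5% | 16% |

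A softer dropout model (logistic in the pre-therapy score, slope 1.5 per SD) agrees. At 20% dropout it gives 0.11 SD, with 6% at 20 per arm and 12% at 50 per arm. At 30% dropout it gives 0.17 SD, with 11% and 24%.

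**Step 4: never-starters in the stated test.** A waitlist subject measured just before delayed therapy, who never starts it, is absent from both sides. If the best 20% are lost, the remaining waitlist has pre mean −0.350r and post mean −0.350rρ. Its apparent gain is 0.350r(1 − ρ) = 0.175r. Pooled with a full early arm, the waitlist's weight is 0.8/1.8 = 0.44, so the gain is 0.04–0.08 SD for r from 0.5 to 1. The false-positive rate is about 2–5%, reaching just under 6% only at 40 per arm with exact selection.

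**Step 5: never-starters in an arm comparison at about eight weeks.** The waitlist mean shifts by the full 0.350r, so early therapy looks better by about 0.17–0.34 SD. False positives are about 13–29% (20 per arm) or 18–47% (40 per arm). If lower-functioning subjects are the ones lost, the sign reverses: the logistic model with 30% lost gives −0.33 SD.

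**Step 6: controls.** With 30% loss unrelated to function (50 per arm), bias is about 0 and the error is 0.016 for pre/post and 0.053 for the arm comparison. With everyone measured at about eight weeks and compared as randomised, bias is about 0.00 SD and the error is 0.048–0.052.

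**Step 7: pairing alone.** A paired test on completers removes the unequal sets but not the selection. By Step 2, their apparent change is 0.350rρ − 0.350r = −0.087 SD (r = 0.5) or −0.175 SD (r = 1), a false loss.

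**The case against.** The strongest reply is that every size above rests on assumed rates and an assumed direction. The document does not say that poor scorers will stop or that recovered subjects will leave the waitlist. Random loss gives no bias, and the opposite selection gives a bias against therapy. This stands: the direction is unknown, and the point is that the rule permits bias, not that it favours therapy.

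Three stronger readings are tempting, and the documents do not support them.

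- **Much larger error rates for the pre/post test.** Rates of 7–23% (n=20), 11–46% (n=40) and 16–65% (n=60) appear only if dropout is driven by the later, unobserved post-therapy score. Dropout that tracks the later score would raise the error, but nothing in the plan supports those figures as the expected size.
- **Never-starters producing a false effect in the stated test.** They are missing from both sides, so their effect is small, and it does not come from the test being unpaired. This assumes that the waitlist's first measurement is taken just before delayed therapy; the document fixes no date. Nor does any rule allow recovered waitlist subjects to skip therapy.
- **The early-versus-waitlist rates as error rates of this plan.** Randomisation to a waitlist makes that comparison natural, but the analysis paragraph does not spell it out.

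A further objection is that natural recovery is the larger problem. Recovery of 0.3 SD per month gives an error of 0.32 in the pre/post test at 20 per arm with no dropout, and about 0.05 in a comparison of arms. That is a separate defect of the same test. It does not remove this one, and it points to the same remedy.

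**Conclusion.** The point holds in a limited form. The stated measurement rule leaves some randomised subjects without a functional outcome, and the stated test compares all starters before therapy with completers after it. This is a weakness in rules the plan does state, not merely a missing detail.

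Under 20% dropout related to the pre-therapy score, the effect on the stated test is modest: roughly a tenth to a sixth of an SD. The error stays at or below nominal when the relation is moderate and reaches 16% at n=60 when it is exact. It grows with sample size and dropout rate. Never-starters matter mainly for an arm comparison at about eight weeks, by about 0.17–0.34 SD if the best-recovered 20% are unmeasured, and in the opposite direction if lower-functioning subjects are lost. None of this arises if loss is unrelated to function. It should be changed, because the remedy is cheap before the trial and unavailable afterwards.

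**What to change.** **Measurement (the paragraphs on therapy and the waitlist).** Give the functional measure to every randomised subject at the four-week session and again at about eight weeks post-injury, whether or not therapy was started or completed. Keep the waitlist's end-of-therapy measurement.

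**Analysis (the t-test paragraph).** Replace the unpaired pre/post test with a comparison of the randomised arms at about eight weeks, with all subjects in their assigned arm. Adjust for the four-week score, or use a mixed model with all available scores. Keep any pre/post summary descriptive and do not base it on completers only; a switch to a paired test would not be enough. Report missing scores by arm, with one sensitivity analysis for loss that is not random.

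**Cost.** One extra administration for the waitlist at a session already attended. The real added effort is an eight-week contact for those who stopped or never started, who have no visit then and for whom no payment is stated. The estimate may be less favourable. Therapy content and timing do not change.

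### Forward stepwise selection, the only screening analysis planned, measures neither how well each measure detects persistent symptoms nor how the two- and four-week results differ

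*Combined protocol and SAP*

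**What the plan says.** The document has one section, Procedures and Statistical Data Analyses. Subjects are "scheduled for cognitive and communication screening at two weeks post-injury", and again later: "At four weeks post-injury, the second screening session will be completed". The analysis of these data is given in the paragraph on the longitudinal design: "Results from the screening measures at two and four weeks post-injury will be compared using a forward stepwise selection model procedure", and the purpose is "to determine which of the screening measures best detect persistent symptoms".

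That is all. The section gives no outcome variable, model type, entry rule or list of candidate measures. It does not say whether the two times enter one model or separate models. It plans no sensitivity, specificity, predictive value, AUC or paired comparison of the times.

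Two other statements bear on the point. The one-SD cut is the entry rule for therapy: "Subjects who are below one standard deviation on screening scores will be randomly placed in either early treatment at one month post-injury". The other arm is "a waitlist control group which will receive the same therapy at two months post-injury". The only later check of status in every subject is a phone call: "All subjects will be contacted via phone at six months and 12 months post-injury to ensure resolution of cognitive-communication problems". The document does not link that call to the stepwise model.

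**The concern.** The sentence promises two things: a comparison of results at two and four weeks, and a finding on which measures detect best. The named method supplies neither as a quantity.

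- **Detection.** How well a screen detects is the share of persistent cases it flags and the share of resolved cases it wrongly flags. Entry into a stepwise model depends on incremental significance or fit. A measure can enter easily and still miss most cases.
- **Comparison.** Forward selection asks whether a score adds to those already entered. The two scores on one measure come from the same subjects and probably overlap. If they are rivals in one model, the first to enter can shut out an equally good second.

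At stake is how the result is read. A measure in the final model would be taken for a good screen, and one left out, or a time left out, for a poor one. Neither inference follows from selection.

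**Working it through.** The documents give no sample size, prevalence, correlation, effect size or accuracy figure, so there is none to reproduce. Every input below is an assumption.

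**1. Entry against detection.** Take normal scores, lower being worse, with persistent cases shifted down by d SD. Assume the cut lies 1 SD below the resolved group's mean; the plan does not say which norm its SD refers to. Take 30 persistent and 30 resolved subjects and a two-sided test at 0.05.

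- AUC = Φ(d/√2)
- Sensitivity at the cut = Φ(−1 + d)
- False-positive rate = Φ(−1) = 0.16
- Power from the noncentral t, 58 degrees of freedom, noncentrality d√(30/2)

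| d | Noncentrality | Chance significant | AUC | Cases caught | False positives |
|---|---|---|---|---|---|
| 0.6 | 2.32 | 63% | Φ(0.424) = 0.66 | Φ(−0.4) = 34% | 16% |
| 0.8 | 3.10 | 86% | Φ(0.566) = 0.71 | Φ(−0.2) = 42% | 16% |

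A measure significant 86% of the time still misses 58% of cases at this cut.

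A second model does not take its norm from the resolved group. It is a bivariate-normal score and outcome with prevalence 10% to 40% and correlation 0.3 to 0.7. Sensitivity at −1 SD then runs from 0.23 to 0.61 and specificity from 0.86 to 0.96. A list of selected measures does not say where in that range a measure lies.

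**2. Two times as rivals in one model.** Simulated forward logistic selection: one measure, d = 0.9 at both times (AUC = Φ(0.636) = 0.74), 30% persistent, likelihood-ratio entry at 0.05, 2,000 to 3,000 runs per case. The two times are equally good by construction.

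- n = 60 to 100, correlation 0.6 to 0.75: exactly one time is named in about 86% to 99% of runs, two or four weeks about equally often. Both enter in under 1% to about 14%.
- Correlation 0.5: both enter in 10% of runs at n = 60, 27% at n = 100 and 73% at n = 200.
- Correlation 0.3: both enter in 28% at n = 60 and 58% at n = 100.
- n = 200: both enter in 11% at correlation 0.75, 54% at 0.6 and 95% at 0.3.

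Repeat runs differ by up to about three percentage points. Crowding-out is strong in small samples with high correlation and nearly gone at n = 200 with correlation 0.3.

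**3. Does selection say anything about time?** Take four measures at two times, all eight scores as candidates, 25% prevalence, n = 40 or 80, 150 runs per setting. With equal score-to-outcome correlation (0.4), a two-week score entered first in 52% of runs at n = 40 and 47% at n = 80. With four weeks truly better (0.5 against 0.4), a four-week score came first in 76% to 77%. Order of entry therefore carries some information, but it comes with no estimate or interval, and about a quarter of runs point the wrong way.

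**The case against.** The best reply is that the stated purpose asks which measures, and stepwise selection is a way to choose measures. From the word for comparison and from the one-SD rule, a reader might infer that the study set out to decide when to screen, or to validate that rule as a diagnostic cut. The document supports neither inference. It states no aim about timing, and "Subjects who are below one standard deviation on screening scores" serves only to define who is randomised to therapy. This objection stands, and the point does not rest on those aims.

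A second reply is that crowding-out assumes a reading. The text could equally mean selection run at each time, with the two results then compared. Under that reading the effect in step 2 disappears. The assumed correlations are also not in the document, and scores two weeks apart in early recovery may correlate less. This stands too, so the simulated range is conditional. It would also be too strong to say that selection tells nothing about time, as step 3 shows.

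A third reply is that accuracy measures need a reference status, and none is defined. If the four-week score defines persistence, its own accuracy is circular. If the later phone contacts define it, subjects below the cut in both arms have been treated by then. This is right, and a better analysis method alone does not cure it. But none of the three replies makes stepwise selection yield a detection rate or a time difference.

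**Conclusion.** The concern holds in a limited form. As written, the plan will not quantify how well any measure detects persistent symptoms, nor the difference between two and four weeks. That follows from what forward selection produces and from the absence of any other screening analysis. It needs no numerical assumption.

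The size of the practical harm does rest on assumptions. Under the normal model of step 1, with the cut set from the resolved group, a measure with a 63% to 86% chance of reaching significance catches 34% to 42% of cases. Crowding-out arises only if both times are candidates in one model. With equal AUC of 0.74 and 30% persistent, both times enter anywhere from under 1% to 95% of the time over n = 60 to 200 and correlation 0.75 down to 0.3.

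It would be too strong to say that the study cannot answer these questions. The limit lies in the written analysis. The same subjects are screened twice and followed for a year, so paired accuracy can be estimated once a reference status is stated.

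**What to change.** Replace the sentence on the screening analysis with the following.

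1. **Reference status.** State one definition of persistent symptoms, when and how it is recorded, and that it is not the four-week screening score itself.
2. **Main analysis.** For each measure at each time, report the AUC, and sensitivity and specificity at the existing one-SD cut, with 95% intervals. State which norm the SD refers to.
3. **Comparisons within subject.** Compare measures, and two with four weeks, by paired AUC difference (DeLong or bootstrap) and by McNemar's test at the cut, applied separately among persistent cases (sensitivity) and resolved cases (specificity).
4. **Stepwise selection.** Keep it, if wanted, as exploratory, run separately at each time.
5. **Interpretation.** Report that subjects below the cut in both arms receive therapy before the six- and 12-month contacts, so accuracy against later status is conditional on that treatment.

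The cost is plan wording and modest extra analysis. No further screening sessions are needed. If the phone contacts supply the reference status, they must record it in a defined way, which the plan does not now provide for. The downside is precision. For an assumed sensitivity of 0.80, the Wilson 95% interval is 0.49 to 0.94 with 10 persistent cases, 0.58 to 0.92 with 20, 0.65 to 0.90 with 40 and 0.70 to 0.87 with 80. With few cases the intervals will be wide; a stepwise list has the same uncertainty but does not show it.

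### The screening measures are chosen by one forward stepwise run with no internal validation, so a reader cannot tell stable choices from chance ones

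*Combined protocol and SAP*

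**What the plan says.** The combined protocol and SAP is titled "Cognitive-Communication Screening and Early Therapy for Adults with Concussion/Mild Traumatic Brain Injury", so screening is one of its two subjects. The analysis of screening is a single sentence in the paragraph on the longitudinal design, under Procedures and Statistical Data Analyses. It reads "Results from the screening measures at two and four weeks post-injury will be compared" and continues "using a forward stepwise selection model procedure to determine which of the screening measures best detect persistent symptoms".

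The document gives no model type, entry or stopping rule, candidate list, sample size or validation step. The one quality check on the screening data is inter-rater scoring of 50% of the screenings. That check concerns how items are scored and does not test the selected model.

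Persistent symptoms are named as the target but not defined by instrument, cut-off or time point. The only impairment rule is given for randomisation: "Subjects who are below one standard deviation on screening scores will be randomly placed". Later status is sought by telephone: "All subjects will be contacted via phone at six months and 12 months post-injury to ensure resolution of cognitive-communication problems". Neither is assigned to the stepwise model.

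**The concern.** Forward selection takes the strongest candidate in the data at each step. With several candidates, some enter by chance, and correlated candidates displace one another from sample to sample. A single run yields one list and no indication of how easily another sample would have produced a different one.

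That matters here because the list is the result. Clinicians reading it would take the named measures as the ones to use after concussion. Without validation, a measure that would be chosen in nearly every resample and one that would be chosen in a minority look the same on the page.

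The undefined target is a supporting point. If the response is not fixed in advance, what counts as best can be settled after the data are seen.

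**Working it through.** **1. Is there a figure to reproduce?** No. The document gives no sample size, number of measures, event rate, entry threshold or expected accuracy. Everything below uses assumed inputs and shows direction and plausible size only.

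**2. Chance entry when nothing is real.** For k independent uninformative candidates and entry threshold a, P(at least one passes) = 1 − (1 − a)^k.

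| k | a = 0.05 | a = 0.15 |
|---|---|---|
| 5 | 1 − 0.95^5 = 22.6% | 1 − 0.85^5 = 55.6% |
| 10 | 1 − 0.95^10 = 40.1% | 1 − 0.85^10 = 80.3% |
| 20 | 1 − 0.95^20 = 64.2% | 1 − 0.85^20 = 96.1% |

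The answer depends heavily on the two quantities that the plan leaves open.

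**3. Stability of the list when some measures are real.** Assumed inputs:
- Five measures at two visits, giving 5 × 2 = 10 candidates.
- Correlation 0.4 between measures within a visit, 0.7 for the same measure across visits, and 0.28 for different measures across visits.
- Two real measures, with log-odds 0.8 and 0.6 per SD.
- About 30% events, and logistic forward selection with likelihood-ratio entry at p<0.05.

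The plan asks which measures detect best, not which measure-and-visit combinations. The right unit is therefore the measure: a real measure picked up at the other visit is not an error.

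| n | Correct list found | Correct list missed (100% minus found) |
|---|---|---|
| 40 | 7-11% | 89-93% |
| 80 | 24-31% | 69-76% |
| 120 | 46-49% | 51-54% |

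A truly null measure is kept in roughly 27-31% of studies. The ranges combine two separate sets of runs. With 600 studies per cell, the simulation standard error near 30% is √(0.3 × 0.7 / 600) = 1.9 percentage points, so these are rough figures.

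**4. A different set-up.** Linear-model selection was also run with 5 to 20 candidates, pairwise correlation 0.5 and two real candidates. The right pair was chosen in 3-10% of samples at n=40 and 28-59% at n=100. The mean overlap (Jaccard index) between the lists from two independent samples was 0.15-0.35 at n=40 and 0.38-0.64 at n=100. The direction is the same.

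**5. Accuracy, the secondary issue.** This uses the inputs of step 3, with 1,500 runs per cell, and averages over studies in which something entered.

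| n | Apparent AUC | New-data AUC | Difference |
|---|---|---|---|
| 40 | 0.819 | 0.696 | 0.123 |
| 80 | 0.785 | 0.726 | 0.059 |
| 120 | 0.781 | 0.743 | 0.038 |
| 300 | 0.777 | 0.764 | 0.013 |

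**6. What a whole-selection bootstrap does.** With the same inputs (200 runs of 100 resamples), corrected against new-data AUC was 0.728 v 0.702, 0.727 v 0.724 and 0.733 v 0.745 at n=40, 80 and 120. When every candidate is noise and something has nevertheless entered, the corrected AUC is still 0.648, 0.594 and 0.572 against a truth of 0.50. The correction is then only partial, so selection frequencies are needed as well.

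**The case against.** The strongest reply is that the plan promises a list and no AUC, sensitivity or prediction rule, that it is brief throughout, and that the sample might be large. On that view an exploratory label would be enough, and asking for a bootstrap is preference.

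Much of this stands. A small sample is an assumption. Optimism in AUC concerns an output that the plan does not mention, and it is small at large n. The unit of counting also matters. Scored by measure-and-visit, the same correlated set-up gives a null kept in 39-48% of studies at n=40 to 120, but this counts a real measure chosen at the other visit as a mistake, so the lower figures are the fair ones.

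The point about the label does not stand. A label warns the reader but does not show which listed measures are stable; selection frequencies do.

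Two stronger readings are tempting and should not be drawn:
- A reader might infer that the model has no target at all. The text does name one, persistent symptoms; what is missing is its definition.
- A reader might infer that four-week scores will be used to predict the four-week below-one-SD status, which those scores themselves define. That would be circular, but the document ties the rule only to randomisation and never says it is the response. It does not exclude this use either, so the point supports a safeguard and does not show an error.

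**Conclusion.** The concern holds in a limited form. A single unvalidated forward stepwise run is the whole method for deciding which measures detect best, and the resulting list may include chance measures without any sign of it. Under the assumed inputs, a null measure is kept in roughly three studies in ten, and the correct list is missed in about half or more of studies up to n=120.

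These figures rest on assumed values for the number of measures, their correlations, the event rate, the effect sizes and the entry rule, and on a binary response. They do not estimate the error in this trial, which cannot be computed from the document. Bias in accuracy is secondary. The undefined response is a gap in specification that supports the point but does not carry it. This is a cheap improvement that the sponsor should make, with medium confidence about its size.

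**What to change.** **Main change.** Repeat the entire forward selection in each of at least 200 bootstrap resamples. Report how often each measure is selected, both pooled over the two visits and by visit. If any accuracy is reported, give the optimism-corrected AUC from the same resamples. Describe the list as exploratory pending external confirmation.

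**Supporting change, before analysis.** State the candidate measures, the model type and the entry rule. Define persistent symptoms as one response that is not computed from the same scores used as predictors. Two candidates lie within the planned contacts, and the choice is the sponsor's:
- Two-week scores predicting four-week status. This precedes study therapy, but it uses the same instruments, may partly rank measures by repeatability, and cannot rank the four-week measures.
- Two- and four-week scores predicting resolved or unresolved status at the six-month call. This is separate from the scores but coarse, exposed to loss to follow-up, and comes after therapy in both randomised groups. The waitlist group is "a waitlist control group which will receive the same therapy at two months post-injury", and the course lasts four weeks, so it is scheduled to finish at about three months.

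**Cost.** A little more analysis work and some wording, plus one standard question if the six-month call is used. No visits or subjects are added. Accuracy will look less flattering, and the bootstrap corrects only partly when noise has entered.

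### The only test of the functional outcome compares scores before and after therapy; it states no early-versus-waitlist contrast and no common time point, so as written it is uncontrolled

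*Combined protocol and SAP*

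**What the plan says.** The combined protocol and SAP has one section, Procedures and Statistical Data Analyses. Its fourth paragraph says that subjects more than one standard deviation low on screening at four weeks are "randomly placed in either early treatment at one month post-injury or a waitlist control group", the latter being "a waitlist control group which will receive the same therapy at two months post-injury". Therapy is one session a week for four weeks. On measurement: "Prior to beginning therapy, a functional outcome measure will be administered", and "At the end of therapy, the same outcome measure will be completed".

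The text on the waitlist arm says that its therapy procedures are the same and that "during the one month waiting period following the second screening, subjects will be given other activities that differ from the actual therapy activities".

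The final paragraph gives the only test of the functional outcome: "one tailed, non-paired t-tests will be used to compare pre- and post-therapy functional outcomes". The other analyses do not cover this outcome. The stepwise model concerns the screening measures, the remaining treatment analysis is qualitative, and no comparison is attached to the six- and 12-month calls.

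**The concern.** The design has a concurrent control: a randomised group that spends the waiting month on other activities. The analysis sentence does not use it. It contrasts before with after, and does not say whether the arms are separated, pooled or compared.

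If the same subjects are compared before and after therapy, two things follow.

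- **No control.** Recovery between the two assessments counts as a therapy effect. Selecting low scorers may add some regression to the mean, to the extent that the screening and functional measures share transient error. A significant result could not be told apart from recovery.
- **Wrong error term.** An unpaired test ignores the correlation between a subject's two scores.

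If a between-arm contrast is intended instead, the text does not say which one, so the choice stays open until after the data are seen.

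**Working it through.** **1. When the scores fall.** The therapy start times and the four-week course imply these approximate times post-injury:

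| Arm | Pre-therapy score | End-of-therapy score |
|---|---|---|
| Early | 1 month | 2 months |
| Waitlist | 2 months | 3 months |

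The waitlist times assume that its first score is taken just before its own therapy, as the early arm's is. The only near-concurrent pair from different people is early end-of-therapy and waitlist pre-therapy, both at about two months.

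**2. Plan's own figure.** There is none to reproduce. Sample size, alpha, power, SD, pre/post correlation and recovery rate are not given. Everything numerical below is assumed.

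**3. Pre versus post in one arm, no therapy effect.** Let n be the number of subjects, d the recovery in SD units and r the pre/post correlation. The unpaired statistic divides the mean difference by s√(2/n), but for the same subjects the true standard error is σ√(2(1−r)/n). The statistic is therefore roughly normal with mean d√(n/2) and variance 1−r, and

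P(reject) ≈ Φ[(d√(n/2) − t_crit)/√(1−r)].

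For n = 20, r = 0.5 and d = 0.5, with one-sided 0.05 (t_crit = 1.686 on 38 df): (0.5 × √10 − 1.686)/√0.5 = (1.581 − 1.686)/0.707 = −0.148, so P ≈ 44%. Simulation (200,000 trials per cell) gives 45%. Simulated rejection rates at r = 0.5:

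| n | d = 0 | d = 0.2 | d = 0.5 | d = 0.75 |
|---|---|---|---|---|
| 10 | 1% | 5% | 23% | 49% |
| 20 | 1% | 8% | 45% | 83% |
| 30 | 1% | 11% | 65% | 96% |

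At n = 20, varying r from 0.3 to 0.7 gives 0.2–3%, 4–11%, 44–46% and 79–88%. Rejection reaches 5% at d of about 0.15 (0.08 for r = 0.3, 0.22 for r = 0.7). With no recovery the test errs the other way and is too conservative.

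**4. Both arms pooled.** With 20 per arm, r = 0.5 and recovery of 0.2, 0.5 and 0.8 SD per month, the early arm alone rejects 8%, 45% and 88% of the time. Pooling raises this to 14%, 77% and 99%.

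**5. Early end-of-therapy versus waitlist pre-therapy.** If recovery is equal in both arms it cancels. Simulated rejection is about 5% for 10 to 30 per arm at every recovery value tried.

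**6. Power of that contrast.** For a 0.5 SD effect, one-sided 0.05 (noncentral t):

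| Analysis | 10 per arm | 20 per arm | 30 per arm | n per arm for 80% |
|---|---|---|---|---|
| Unadjusted | 28% | 46% | 61% | 51 |
| Covariate correlating 0.5 with outcome | 34% | 56% | 71% | 38 |

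The second row follows because adjustment scales residual variance by 1 − 0.5² = 0.75, and 51 × 0.75 ≈ 38.

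**The case against.** The best counter-argument is the word non-paired. It describes a comparison of different people, and beside a randomised waitlist it may mean that a between-arm test was intended. That is a fair reading, and on the schedule above it is a valid one. It does not rescue the text, because the contrast is never stated.

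A third reading compares pre-to-post change between arms. It uses the randomised groups, but over different periods (about months one to two against two to three). Any difference in recovery rate between those periods would be confounded with arm, and both changes include therapy.

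Three narrower points deserve weight.

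- The week of the waitlist arm's pre-therapy score is not written down. A score taken at four weeks, before the waiting month, would also precede therapy. The later date is the natural inference from the shared therapy procedures, but it should be fixed in the text.
- Selection is on screening scores, not on the functional outcome, so regression to the mean may be small. Recovery alone carries the argument.
- All rejection rates rest on assumed inputs. At the lowest recovery values they run from 1% to 11%.

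**Conclusion.** The concern holds: the analysis is wrong as written and must be fixed. The only efficacy test of the functional outcome names neither a between-arm contrast nor a common time, and on its plain reading it cannot separate therapy from recovery. The defect lies in the analysis text; the design can support a controlled comparison.

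The false-positive rate for this trial cannot be derived. Under the stated assumptions it runs from below the nominal level with no recovery to well above it with moderate recovery. The 5% rate of the concurrent contrast depends on equal recovery in both arms, which randomisation supports, and on scoring both arms at the same time since injury.

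**What to change.** State as the primary efficacy analysis the between-arm comparison at about two months post-injury: early-arm end-of-therapy functional score against waitlist-arm pre-therapy functional score. Then:

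- Analyse by randomised group.
- Set one assessment window for both arms, so that the waitlist score is taken at the end of the waiting month.
- Preferably adjust for one four-week screening measure named in advance, or for the single score rule that defines eligibility. There are several screening measures, and no four-week functional score is clearly scheduled for the waitlist arm. Adjustment improves precision; the concurrent contrast is what cures the defect.
- Report within-arm pre-post change as descriptive only, with a paired method.

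The cost is analysis wording, a named covariate and a fixed window. No measurement is added, since each arm already has the functional score that the contrast needs. The apparent effect will probably be smaller than a pre-post change, and power is limited as shown above. No sample size is stated, so whether enrolment suffices cannot be judged, and the plan should say so. The controlled comparison also ends at about two months, when the waitlist arm starts the same therapy.
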